8.3 Procedures at each visit

8.3.1 Visit 1

- Patient screening and eligibility assessment in the Polyclinic for Chiropractic Medicine by an Investigator
- Patient will be contacted and asked if he would like to participate 3-4 days after screening.
- Patient is sent informed consent and general consent, which he will return signed.
- An appointment is made for Study Visit 2

- Controls will contact one of the investigators by the number provided on the flyer. Control is sent informed consent and general consent, which he will return signed. An appointment for study visit 2 is made.

8.3.2 Visit 2

- Inclusion and exclusion criteria are checked.
- Demographics and baseline Information is collected by an Investigator. Oswestry Disability Index and painDetect questionnaires are administered.
- A physical examination including vital signs, lower extremity neurological examination, and lumbar spine examination is performed by an Investigator.

- Subjects consenting to venipuncture will proceed to the venipuncture site, where 10-15 ml of whole blood will be drawn from the vein (usually at the elbow) using serum collection tubes. Blood samples are allowed to clot at room temperature for 30-60 min and then centrifuged at 2500 x g for 10 min at 4°C. The resulting serum supernatant is stored in aliquots at Balgrist Campus first at -20°C and transferred within 2-20 hours to -80°C.
- Subjects will prepare for MRI, which will be performed under the supervision of a radiographer. The first sequence of MR-imaging takes approximately 20 minutes.
- Randomisation takes place.
- Patients exit the scanner and receive either an intervention or a control intervention, depending on the randomisation result.
- Controls exit the scanner and lie supine for 20 minutes.
- All subjects reenter the scanner and proceed to have a second round of imaging.
- Patients are assessed for pain and vital signs. They may then leave the study site.
- Controls may also leave the study site, and go on to lead their normal daily lives (excluding strenuous physical activity) for the next 10 hours. They then report back to the University Hospital Balgrist for their third and last MRI. After this, they are also assessed for pain and vital signs. This marks the end of the study for controls.

8.3.3 Visit 3-5

- At one week, patients are contacted by online questionnaire. Patient's global impression of change is recorded. The Oswestry Disability Index and the painDetect-questionnaire are repeated; pain parameters, and type and frequency of concomitant therapies are assessed.
- At one month, the same online questionnaire will be repeated.
- At three months, the same online questionnaire will be repeated. The three month interview marks the end of the study for patients.

9. SAFETY

Serious adverse events (ICH E6 1.2, ICH E2A) will be documented and notified as described in ClinO Art.63: If, in the course of a clinical trial, serious adverse events (SAEs) occur in participants in Switzerland, and it cannot be excluded that the events are attributable to the intervention under investigation, the investigator will document them in a standardised manner. In addition, the investigator will report these events:

- a.) to the sponsor within 24 hours after they become known; and
- b.) to the responsible ethics committee within 15 days

SAEs in which a relation to the study intervention cannot be excluded will be noted in the electronic case report form (eCRF) and a SAE form will be completed. During the entire duration of the study, all SAEs in which a relation to the study intervention cannot be excluded are collected, fully investigated and documented in source documents and eCRF. Study duration encompassed the time from when the participant signs the informed consent until the last investigation plan-specific procedure has been completed. Considering that the study-specific interventions are standard-of-care and performed for many decades standard safety measures of clinical routine apply and no further safety follow-up is needed.

No drugs or other products are administered during the study. Study-related severe adverse events associated to medical drugs or products are not expected.

9.1 Other Clinical Trials

9.1.1 Definition and Assessment of Safety Related Events

Adverse Event (AE)

Any untoward medical occurrence, unintended disease or injury or any untoward clinical signs (including an abnormal laboratory finding) in participants, that occurs after an intervention whether in causal relation with this treatment or not.

Serious Adverse Event (SAE)

Adverse event that:

- requires inpatient treatment not envisaged in the protocol or extends a current hospital stay;
- results in permanent or significant incapacity or disability;
- is life-threatening or results in death; or
- causes a congenital anomaly or birth defect

In addition, important medical events that may not be immediately life-threatening or result in death, or require hospitalisation, but may jeopardise the patient or may require intervention to prevent one of the other outcomes listed above should also usually be considered serious. [ICH E2A]

SAEs are followed until resolution or stabilisation. Participants with ongoing SAEs at study termination will be further followed up until recovery or until stabilisation of the disease after termination.

Health hazards that require measures

Findings in the trial that may affect the safety of study participants and, which require preventive or corrective measures intended to protect the health and safety of study participants.

Assessment of Causality

Both Investigator and Sponsor-investigator make a causality assessment of the event to the intervention, based on the criteria listed in the ICH E2A guidelines:

Relationship	Description
Definitely	Temporal relationship Improvement after dechallenge* Recurrence after rechallenge

	(or other proof of intervention cause)
Probably	Temporal relationship Improvement after dechallenge No other cause evident
Possibly	Temporal relationship Other cause possible
Unlikely	Any assessable reaction that does not fulfil the above conditions
Not related	Causal relationship can be ruled out
*Improvement after dechallenge only taken into consideration, if applicable to reaction	

Assessment of Severity

The severity grading scale used for this study will be the “Common Terminology Criteria for Adverse Events CTCAE Version 4.02”⁴⁷.

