Intravoxel incoherent motion (IVIM) is a method proposed in 1988 by Le Bihan et al. which extracts microvascular blood flow information from diffusion-weighted imaging acquired at different b-values^{19,20}. It is used to generate separate images of diffusion and perfusion without requiring the injection of exogenous contrast agents. Originally developed in brain studies, it has been used in recent years to study perfusion in musculoskeletal tissue^{21,22}. There is a paucity of research addressing physiological events following a SMT intervention for patients with low back pain¹⁷. A deeper understanding of local biomechanical and neurophysiological effects of SMT interventions might help refine its utilization and improve its effectiveness²³.

The purpose of our study is to quantify changes in diffusion and perfusion parameters within the intervertebral disc and paraspinal muscle tissue of a spinal segment receiving a spinal manipulative intervention and to evaluate whether those changes differ in spinal segments with or without degenerative changes in symptomatic and asymptomatic subjects.

Additionally, it is of interest to determine the relationships between baseline parameters and changes in diffusion and perfusion as well as the degree of degenerative changes. Post-intervention changes in segmental spinal muscle perfusion will also be investigated.

The repeatability and diurnal variation of IVIM imaging in quantifying perfusion in musculoskeletal tissues will be assessed by comparing perfusion parameters of 20 controls who will not receive any intervention. We will perform a diffusion- and perfusion-weighted MRI at the beginning of the visit in the morning, which is repeated after approximately 20 minutes of rest (lying supine). Controls will present for an additional MRI approximately 10 hours later in the evening of the same day.

In participants consenting to venipuncture, approximately 8 ml of venous blood will be withdrawn using serum collection tubes, allowed to clot, and then centrifuged. The resulting serum supernatant is stored in aliquots at Balgrist Campus at -80°C. It will be analysed at the end of data collection for pro- and anti-inflammatory markers (e.g. C-reactive Protein, Interleukin 1-beta, Interleukin 6 and Tumor Necrosis Factor) in order to determine the relationship between inflammatory markers and degenerative changes, pain duration, and pain and disability outcomes³⁹.

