8.2.4 Assessment of safety outcomes

Patients' vital signs and pain intensity will be assessed before and after the experimental procedure and recorded according to clinical standards. The patient will be able to verbally communicate discomfort or pain at any time during the experimental procedure.

8.2.4.1 *Adverse events*

Time of onset, duration, resolution, action to be taken, intensity and relationship with SMT intervention of adverse events are going to be recorded according to clinical standards. Participants are going to be assessed for adverse events according to current standard of care after the experimental procedure.

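### The safety sections disagree on which events count: the adverse event definition starts after an intervention, collection starts at consent, and MRI and venipuncture are not named in the causality question

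*Combined protocol and SAP*

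**What the plan says.** **Definition.** Section 9.1.1 counts an untoward occurrence "in participants, that occurs after an intervention whether in causal relation with this treatment or not". The same section defines an SAE as an adverse event that meets further criteria, so SAEs inherit this starting point.

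**Collection window.** Section 9 collects SAEs over the whole study and adds: "Study duration encompassed the time from when the participant signs the informed consent until the last investigation plan-specific procedure has been completed". The study schedule ticks the adverse event row at -45, -15, 0 and +5 minutes and at 7, 30 and 90 days. The SMT or control intervention is at time 0.

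**Causality.** Section 8.2.4.1 says that "intensity and relationship with SMT intervention of adverse events are going to be recorded". Section 9.1.1 says: "Both Investigator and Sponsor-investigator make a causality assessment of the event to the intervention". Sections 9 and 10.1.2 require eCRF entry, notice to the sponsor within 24 hours and notice to the ethics committee within 15 days only for SAEs whose link with the study intervention cannot be ruled out.

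**Healthy controls.** Section 3.1 describes "comparing perfusion parameters of 20 controls who will not receive any intervention". They have three MRI scans and an optional blood draw. For the visit that ends with the third scan, section 8.3.2 states: "After this, they are also assessed for pain and vital signs. This marks the end of the study for controls". In the schedule, the +10 hour column that holds this scan is blank for both vital signs and adverse events.

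**The concern.** The definition, the collection window, the causality question and the schedule each draw the boundary of a reportable event differently. Staff are told to look for events at times when, by the definition, no adverse event can yet exist. Those who judge causality are asked about SMT in one section and about an undefined intervention in the others.

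The MRI scans and the optional blood draw are done for the study, and section 3.7 itself describes hazards of the MR environment. The plan has no other safety structure to fall back on: sections 3.12 and 4.4 mark safety objectives and outcomes as not applicable, and section 1.6 does the same for a safety monitoring committee. The event definition and the SAE filter therefore carry most of the safety plan. At stake is whether harm from a study procedure, or harm in a healthy volunteer, is recorded and reported in the same way as harm from SMT.

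**Working it through.** The plan gives no figure to reproduce here, so the check sets the sections side by side.

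**Step 1: what *intervention* means in the operative text.**
- Section 5.1 places the first scan of patients and controls before the intervention.
- Sections 7.1.1 and 7.1.2 define two interventions: SMT and the positioning-only control procedure.
- Section 8.3.2 has patients leave the scanner and then receive one of these two.
- Section 3.1 says the healthy controls receive none.

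The one departure is section 13.1 (Funding), which uses the term for the MRI.

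**Step 2: apply the rules, with *intervention* meaning SMT or sham.**

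| Event | Within the 9.1.1 definition? | Adverse event row ticked? | SAE passes the relatedness filter in 9 and 10.1.2? |
|---|---|---|---|
| Patient, blood draw or examination (-45 min) | No | Yes | No |
| Patient, first MRI (-15 min) | No | Yes | No |
| Patient, MRI after the intervention, harm clearly due to the scan | Yes | Yes | No |
| Patient, harm possibly due to SMT | Yes | Yes | Yes |
| Control, blood draw, first or second MRI | No | Yes | No |
| Control, third MRI (+10 hours) | No | No | No |

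The two restrictions act separately. The third row shows that moving the time window alone would not be enough, because a harm clearly caused by the scanner would still be judged unrelated to the study intervention.

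**Step 3: try the wider reading.** If the usage in section 13.1 is applied throughout, the window opens at the first MRI, for controls as well. The blood draw and the examination still come before it, and I find no section that calls either of them an intervention. The wider reading narrows the gap but does not close it.

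**Step 4: who is touched.** Section 10.2 gives 25 + 25 + 20 = 70 participants. All 50 patients have an examination and a first scan before time 0. The 20 controls have 20 × 3 = 60 scheduled scans, of which the 20 at +10 hours have no adverse event or vital sign tick.

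**Step 5: other routes for an SAE.** Section 10.1.2 puts observed or volunteered SAEs in the patient file whatever the group or presumed cause. Section 2.3 requires unforeseen problems that put people at risk to be reported. Section 10.1.2 also sends urgent safety measures and what caused them to the ethics committee within seven days. A procedure-related SAE would thus be on file and might be reported under section 2.3, but the rules as written do not take it to the eCRF or into the 24-hour and 15-day reports.

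**The case against.** The strongest reply is that nothing in the plan expressly excludes controls or procedure-related harms. The adverse event row carries no patients-only label, while other rows are labelled by group where they differ. Section 10.1.2 questions study participants about adverse events at visits, and section 8.2.4.1 says: "Participants are going to be assessed for adverse events according to current standard of care after the experimental procedure". Section 9.1.1 speaks of an unspecified intervention, and section 10.1.2 mentions action taken with a study-related procedure. The relatedness filter is a stated choice that follows the ordinance as section 9 describes it, for a study that section 2.2 classes as minimal risk.

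Much of this stands, and it rules out several stronger readings that a reader might infer:
- *That 20 of 70 participants (28.6%) cannot have an adverse event, or that the annual report must show none in controls.* This joins a background sentence to a safety definition, and the plan does not state what the annual report contains.
- *That pain flares before the intervention go unrecorded.* The schedule collects adverse events at both earlier times.
- *That causality is judged only against SMT throughout.* Only section 8.2.4.1 says so.
- *That procedure-related SAEs vanish.* They reach the patient file and possibly the section 2.3 route.

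The reply does not remove the inconsistency. The mention of a study-related procedure describes details for SAEs that have already passed the relatedness filter. The patient-file rule covers SAEs only, so non-serious events have no such safeguard. The mismatch at +10 hours needs no interpretation: section 8.3.2 takes vital signs that the schedule does not show.

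**Conclusion.** The point holds as an inconsistency that should be reconciled. It is not a finding that any group is shut out of safety monitoring. The definition, the window, the causality wording and the schedule cannot all be applied as written. On the usage in sections 3.1, 5.1, 7.1 and 8.3.2, pre-intervention procedure harms and events in the 20 controls fall outside the definition, and an SAE due to MRI or venipuncture has no stated path to the eCRF or the expedited reports.

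This rests on *intervention* meaning SMT or sham. If MRI is included, the gap shrinks to the blood draw and the examination, and the undefined term is then itself a reason to define it. The +10 hour contradiction stands on either reading. No primary estimate, power figure or error rate depends on this. What is at stake is the completeness and consistency of safety data, at very little cost to correct.

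**What to change.** 1. In section 9.1.1, define an adverse event as any untoward occurrence from signed consent to the last study contact, in patients and in healthy controls.
2. In sections 8.2.4.1, 9, 9.1.1 and 10.1.2, use one causality question: relation to SMT, the control procedure or any study procedure, including MRI and venipuncture. Apply the same wording to the filter for eCRF entry and for SAE reports.
3. In the study schedule, tick adverse events and vital signs at +10 hours for controls, to match section 8.3.2.

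Reporting events before and after randomisation separately would be useful but is optional.

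The cost is protocol wording, a matching causality field in the eCRF and two ticks in the schedule. No visit or procedure is added. The downside is a few more minor events to record.

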10.1.2 Reporting of serious adverse events (SAE) and other safety related events

Reporting of SAEs

Clinical investigators and ultimately the Principal Investigator (PI) have the primary responsibility for SAE identification, documentation, grading, and assignment of attribution to the intervention under study.

Clinical study participants will be routinely questioned about AEs at study visits. The well-being of the participants will be ascertained by neutral questioning ("How are you?").

Observed or volunteered SAEs, regardless of treatment group or suspected causal relationship to the study treatment(s) will be recorded in the patient file and subsequently in the eCRF if a relationship to the study intervention cannot be excluded.

All SAEs in which a relation to the study intervention cannot be excluded, will be fully documented in the appropriate eCRF. For each such SAE, the investigator will provide the onset, duration, intensity, treatment required, outcome and action taken with the investigational device or study related procedure.

The investigator shall report these events:

- a.) to the sponsor within 24 hours after they become known; and
- b.) to the responsible ethics committee via BASEC within 15 days

Periodic reporting of safety

An annual safety report is submitted once a year to the local Ethics Committee via local Investigator.

Art.37 par. 1 KlinV Safety measures

Urgently applied safety measures during the study period as well as causing factors are going to be reported to the EC within a time period of seven days.

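### SAEs judged unrelated stay out of the eCRF and the sponsor report, with no stated route to the second causality assessor that section 9.1.1 requires

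*Combined protocol and SAP*

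**What the plan says.** Three parts of the safety chapter bear on this point.

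- **Section 9 (Safety)**, citing the Swiss clinical trials ordinance, ties standardised documentation to relatedness: where "it cannot be excluded that the events are attributable to the intervention under investigation, the investigator will document them in a standardised manner". The eCRF entry and the SAE form carry the same condition.
- **Section 10.1.2 (Reporting of SAEs)** opens broadly: SAEs go into the patient file whatever the arm or suspected cause. It then narrows: "subsequently in the eCRF if a relationship to the study intervention cannot be excluded". Only the events that pass are reported "to the sponsor within 24 hours after they become known", and to the ethics committee within 15 days. On who decides, it says: "Clinical investigators and ultimately the Principal Investigator (PI) have the primary responsibility for SAE identification, documentation, grading, and assignment of attribution".
- **Section 9.1.1 (Definition and Assessment)** says: "Both Investigator and Sponsor-investigator make a causality assessment of the event to the intervention". The scale has five categories. The last, Not related, is defined as "Causal relationship can be ruled out". Nothing confines the double assessment to events already thought related.

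Safety objectives (3.12) and safety outcomes (4.4) are marked not applicable, and the statistical chapter plans no analysis of SAEs.

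**The concern.** A double causality assessment protects against a single mistaken judgement, and the dismissal of an event as unrelated is one of the judgements it should cover. Here relatedness is also the entry condition for the eCRF, the SAE form and the sponsor report. The events most in need of a second look are those for which no transmission is laid down.

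The database matters too. Section 11.1 says study data are held exclusively in REDCap, so an SAE left out of the eCRF is outside the trial dataset. Section 3.7 lists disc herniation and cauda equina syndrome among the serious events reported after lumbopelvic SMT, and notes that the reports could not settle causality or incidence. Randomised arms help with that question only if events are counted without regard to attribution. Section 2.9 also allows the trial to stop on early evidence of harm, and section 1.6 provides no data safety monitoring committee. A complete SAE record in the trial database therefore carries more weight than usual.

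**Working it through.** **No plan figure to reproduce.** The documents give no SAE rate, no expected count and no SAE comparison. The check is a comparison of text, followed by an illustration whose rates are assumptions.

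**Step 1: follow an SAE judged Not related.**

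| Destination | Condition in the protocol | Reached? |
|---|---|---|
| Patient file (10.1.2) | None | Yes |
| Standardised documentation (9) | Relation cannot be excluded | No |
| eCRF and SAE form (9, 10.1.2) | Relation cannot be excluded | No |
| Sponsor within 24 hours (9, 10.1.2) | Same events only | No |
| Sponsor-investigator's causality assessment (9.1.1) | None stated | No route stated |

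The last row conflicts with the rows above it. Section 9.1.1 requires the second assessment, and sections 9 and 10.1.2 provide no step that delivers the event.

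**Step 2: which categories are stopped.** Only Not related means that causality is ruled out. On a plain reading, Definitely, Probably, Possibly and Unlikely all pass. The gap is one category out of five.

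**Step 3: could dismissal differ by arm?** Three features make that plausible:

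- Section 8.2.4.1 records the relationship of adverse events to SMT, which control patients do not receive.
- Section 7.1.2 describes a control procedure without pressure, preload or thrust.
- Section 5.2.2 blinds the examiner and radiologist but does not say that whoever judges SAE causality is blinded. Patients are not blinded.

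**Step 4: illustration.** Take 25 patients per arm (section 10.2), the same true SAE risk p in both arms, and a share r of SAEs that passes the condition. Then expected eCRF SAEs per arm = 25 × p × r. All p and r values are assumptions. With p = 2%:

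| r in SMT arm | r in control arm | SMT arm | Control arm |
|---|---|---|---|
| 1 | 1 | 25 × 0.02 × 1 = 0.50 | 0.50 |
| 0.5 | 0.5 | 25 × 0.02 × 0.5 = 0.25 | 0.25 |
| 0.5 | 0.25 | 0.25 | 25 × 0.02 × 0.25 = 0.125 |
| 1 | 0 | 0.50 | 0 |

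In the extreme last case, p = 1% gives 0.25 against 0, and p = 4% gives 1.0 against 0. The chance of at least one SAE among the 50 patients is 1 − (1 − p)^50: 39.5% for p = 1%, 63.6% for 2% and 87.0% for 4%.

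If the same share passes in both arms, expected counts are too low but equal. They separate only if dismissal differs by arm.

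**The case against.** The strongest reply is that no SAE is lost. Every one is in the patient file, section 2.8 gives the sponsor's representatives access to relevant medical records, and section 11.3.1 includes SAEs in the monitor's checks. A reader might infer that the second assessment cannot happen at all. The documents do not support that: nothing bars the sponsor-investigator from assessing an event in the file, and 9.1.1 could be read as both assessors judging before the condition is applied. What remains is that no passage sets out that order, route or timing, and that the monitor's SAE check covers the first participant and at least 10% of those recruited, not everyone.

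A reader might also infer that the sponsor's review can lower an attribution but never raise one. That is wrong as stated, because an Unlikely event passes and can be raised. It is true only of Not related events, and there only in the sense that no route is given. Nor is it certain that one investigator's view decides, since 10.1.2 gives final responsibility for attribution to the principal investigator.

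Third, the rule is said to follow the ordinance, and section 2.2 classes the trial as minimal risk with a standard intervention. Both are fair context. The ordinance itself was not checked. The mismatch between sections stands without it, and a reporting duty owed to an ethics committee does not prevent fuller recording inside the trial.

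**Conclusion.** The point holds as an internal inconsistency with a practical consequence. Sections 9 and 10.1.2 make eCRF entry, the SAE form and sponsor reporting depend on relatedness, while 9.1.1 requires two assessments without that limit. SAEs judged Not related would be missing from the trial database, and their second assessment has no stated path.

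The size cannot be fixed from the documents. At assumed risks of 1% to 4% the expected number of SAEs is at most 1.0 per arm, so few events are at stake, but one omission could be the whole record.

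Two stronger readings should be resisted. One is that counts by arm are skewed. That needs unequal dismissal, which the wording makes plausible but does not show; the control procedure also positions the patient on both sides and is itself described under Study Intervention, so the condition can be read to cover it. The other is to measure the harm by a confidence limit that widens when an omitted event is restored. A limit for related SAEs and a limit for all SAEs are different quantities, restoring an unrelated event changes only the second, and the plan calls for neither.

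No planned analysis is affected, and the harm criterion in section 2.9 has no numerical rule tied to eCRF counts. The consequence is for safety reporting.

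**What to change.** 1. In sections 9 and 10.1.2, enter every SAE from consent to the last study contact in the eCRF with an SAE form, whatever the suspected cause.
2. Send each one to the sponsor-investigator, so that the second assessment in 9.1.1 can be made on all of them.
3. Keep the condition that a relation cannot be excluded only for the 15-day report to the ethics committee, so that this duty does not change.
4. In the final report, list all SAEs by arm descriptively, with the related subset shown separately. No test is needed.

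The cost is revised wording in two sections and a few more SAE forms. The events are already written in the patient file, so no new data are collected from participants.
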